6.1 CRITERIA FOR SUBJECT ELIGIBILITY

6.2 Subject Inclusion Criteria

- Histologically-confirmed (confirmation done at MSKCC) metastatic adenocarcinoma of the breast
- Radiologic evidence of new and/or progressive brain metastases (≥ 10 mm in longest dimension) by MRI imaging of the Brain
- Planned WBRT based on number (≥ 3 lesions) and/or size (≥ 1 cm) of brain metastases.
- Age ≥ 18 years; males and females
- Patients who require additional clinically indicated stereotactic radiosurgery (SRS) in addition to WBRT will also be eligible.
- Life expectancy of >12 weeks.
- Karnofsky Performance Status (KPS) $\geq 70\%$.
- Creatinine ≤ 2.0 times the upper limit of normal.
- Women of childbearing potential must have a negative serum pregnancy test performed within 7 days prior to enrollment, must be non-lactating and must agree to use adequate contraception prior to enrollment and for the duration of study participation.
- No limit to prior therapies with last anti-cancer treatment ≥ 2 weeks from initiation of WBRT. Please note: there is no washout period required for trastuzumab, pertuzumab for patients who have developed new parenchymal brain metastases while on these agents.

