12.1 Measurable lesion

In the presence of multifocal disease, up to five bi-dimensionally measurable enhancing mass lesions will be followed for objective response. The bidimensional perpendicular measurements for each lesion should always be assessed in the same plane of axis (axial, coronal, sagittal or other). The largest perpendicular diameters of enhancement for each mass lesion will be recorded. Any and all remaining enhancing lesions will be followed as a single site and classified as an evaluable lesion. Objective response of the measurable lesion will be assessed by comparison of the changes in the product of the largest perpendicular measurements of the lesion at each visit. Comparisons of objective assessments for a measurable lesions(s) excluding progressive disease, are based upon major changes in tumor size on the Gd-MRI scan compared to the baseline scan. Determination of progressive disease is based upon comparison to the previous scan with the smallest measurements. Comparisons should always be made with measurements assessed in the same plane of axis (axial, coronal, sagittal or other).

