12.3 Criteria for current objective status

At each tumor assessment visit the current objective status is determined. This takes into account measurable and evaluable lesion(s). Comparisons of assessments for measurable and evaluable lesions, excluding progressive disease, are based upon major changes in tumor size on Gd-MRI scan compared to the baseline scan. The assessment is adapted from Macdonald et al. Determination of progressive disease is based upon comparison to the previous scan with the smallest measurements. Scan changes are emphasized, but are interpreted in light of steroid use and to a lesser extent, neurological findings. Categories of overall response include:

Complete response (CR): Disappearance of all enhancing tumor on consecutive MRI scans at least one month apart, off steroids and neurologically stable or improved. No new lesions may arise.

Partial response (PR): Greater than or equal to a 50% reduction (< 100%) in the sum of the products of the largest perpendicular diameters of contrast enhancement for measurable lesions and if an evaluable lesion(s) is present at baseline, no worsening for an evaluable lesion(s) on consecutive Gd-MRI scans at least one month apart, steroids stable for 72 hours prior to each scan at the same dose administered at the time of the previous scan or at a reduced dose, and neurologically stable or improved. No new lesions may arise.

Progressive disease (PD): Greater than or equal to a 25% increase in size of the product of the largest perpendicular diameters of contrast enhancement for any measurable lesions or if an evaluable(s) lesion is present at baseline, worsening for an evaluable lesion(s) or any new tumor on Gd-MRI scans or greater than or equal to 25% increase in the unidimensional measurement of the any lesion in an additional plane of axis, steroids are stable for 72 hours prior to each scan at the same dose administered at the time of the previous scan or at an increased dose, with or without neurological progression. The following will also apply:

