12.4.1 Determination of best response

The best response for each patient is determined from the sequence of objective statuses according to the following rules:

CR = at least two determinations of CR a minimum of 4 weeks apart before progression, preceded by lower statuses, or preceded, separated or followed by unknown statuses.

PR = at least two determinations of PR or better a minimum of 4 weeks apart before progression (but not qualifying for CR), preceded by lower statuses, or preceded, separated or followed by UNK statuses.

SD = at least one determination of stable disease or better

PD = a determination of progression in one of the first two assessments

UNK = the status is UNK only if all assessments before progression are UNK.

If there is a defined objective that includes the assessment/measurement of therapeutic response to the defined treatment intervention, then detailed description of the measure, methods to be used (e.g., scales and/or definitions to assess response) and the criteria to determine each level of therapeutic response should be included.

FLT-PET

Response assessment for FLT-PET will be as follows:

SUV max and average (42% threshold) for brain lesions will be measured (for FLT using summed images 45-60min). In addition, we will explore other measures such as metabolic tumor volume. For comparison, activity will also be measured in remote normal cortex and white matter. Tumor - to-normal ratios will be computed. Treatment induced changes in these parameters will be expressed as % decrease in radiotracer uptake. Tentatively, a decline by 25% [26] will be considered significant.

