14.0 BIOSTATISTICS

This is a small pilot study involving 20 patients with brain metastases from breast cancer. The first cohort will include the first ten patients that are enrolled to a separate but simultaneous phase I study evaluating patients receiving concurrent sorafenib + whole brain radiotherapy (WBXRT). *The goal of the phase I study is to determine the MTD of sorafenib in breast cancer patients with brain metastases receiving WBRT.* Ten additional patients who do not enter the parallel phase I trial and receive WBXRT without sorafenib, will be consented to this imaging study. Both cohorts have the same eligibility criteria.

The first ten patients recruited into the Phase I trial of sorafenib + whole brain radiotherapy will have to agree to consent to the FLT-PET imaging study. The cohort receiving WBRT alone will be recruited independently.

The primary objective of this study is to examine radiographic response to WBRT by two modalities: FLT-PET and MRI. MRI is considered standard of care and response assessments are recorded as

CR, PR, PD, SD, and unknown (see section 12.0). FLT-PET response assessments will be recorded as SUV-MAX and a decline by 25% is considered as significant (see Section 12.0). MRI measurements will be recorded at baseline and 10 to 12 weeks post WBRT. FLT-PET measurements will be recorded at baseline, 10 days post WBXRT, and 10-12 weeks post WBXRT.

This is a small pilot study and as such, we are limited in the scope of our analyses by sample size. Data from each modality will be examined descriptively and graphically at baseline and over the course of treatment. Specifically, the distribution of response at baseline and the 10-12 week post WBXRT timepoint as assessed by MRI and FLT-PET will be examined. The median, mean, min and max of SUV max for FLT-PET will be summarized at each timepoint. Significant or nonsignificant change in SUV from baseline to the 10-12 weeks post WBRT timepoint (decline by 25%) will also be calculated and the frequency of patients with significant change will be calculated. These descriptive analyses will be done for each cohort separately. Because FLT-PET can be used to assess early treatment response, SUV values and significant SUV change from baseline to 10 days post WBRT will be examined descriptively.

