As written in Section 10.1, FLT-PET imaging provides assessments in addition to SUV. These additional assessments are kinetic rate constants based on a compartmental model. These parameters will also be analyzed using the approach described above (median, mean, min and max summarize at each timepoint for each cohort). .

Based on these analyses, we will explore whether treatment response for the two modalities correlate To compare the two modalities, the proportion of patients with significant change in SUV (FLT-PET) as a dichotomous variable, will be calculated in the following two MRI response groups: CR+PR vs. PD+SD. The McNemar's test for paired samples will be done to test the agreement of the two modalities. In addition, boxplots of SUV will be graphed for each MRI response category for each cohort. Based on the literature in this patient population, there is a 65-70 percent response rate as per MRI. Median duration of response will be calculated and summarized overall and for each cohort separately.

Any clinical, tissue, or other correlations are entirely exploratory in nature. It is expected that 2 patients will be accrued per month, with accrual for all 20 patients taking approximately 1 year.

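### FLT-PET and MRI are formally compared only as one yes/no per patient, with no stated rule for combining lesion SUVs; a continuous analysis at patient and lesion level would cheaply recover power and separate roll-up effects from real disagreement

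*Combined protocol and SAP*

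**What the plan says.** **MRI.** Section 12.1 states that "up to five bi-dimensionally measurable enhancing mass lesions will be followed for objective response"; any others are followed together as one evaluable site. Section 12.3 rolls these up to one status per patient. Partial response needs "Greater than or equal to a 50% reduction (< 100%) in the sum of the products of the largest perpendicular diameters", no new lesion, no worsening of evaluable disease, and confirmation. Progression can come from a single lesion: a "25% increase in size of the product of the largest perpendicular diameters of contrast enhancement for any measurable lesions". Any new enhancing tumour also counts as progression.

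**FLT.** The FLT-PET text at the end of Section 12.4.1 says "SUV max and average (42% threshold) for brain lesions will be measured" and tentatively treats a 25% decline as significant. Section 14.0 records the FLT response as SUVmax with the same cut. No section says how many lesions are measured on FLT, whether they are the MRI target lesions, or how several lesion values become one patient value. There is no FLT rule for a new lesion.

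**Comparison.** Section 14.0 uses "the proportion of patients with significant change in SUV (FLT-PET) as a dichotomous variable", split by CR+PR against PD+SD, with McNemar's test. It adds SUV boxplots by MRI category for each cohort. No matched-lesion or clustered analysis is described.

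**Lesions per patient.** Section 6.2 requires "Planned WBRT based on number (≥ 3 lesions) and/or size (≥ 1 cm) of brain metastases", so patients with one lesion and patients with several can both enter.

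**The concern.** Secondary objective 1 (Section 2.1) correlates FLT response with MRI response. Section 14.0 says its analyses are limited by sample size, yet the formal comparison reduces two continuous measurements, often on several lesions, to one binary value each.

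Two things are at stake. The first is power: a 2x2 table of 20 patients can show only a very strong association. The second is interpretation. If a patient is an FLT responder and an MRI non-responder, the table cannot say whether the scans disagreed about the same metastases or whether the roll-up rules produced the difference.

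**Working it through.** The plan gives no power or precision figure for this comparison, so there is nothing to reproduce. The checks below use its thresholds and its 20 patients. The remaining inputs are assumptions.

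**1. An example from the plan's thresholds.** Take five target lesions with equal baseline product P. Four disappear and one grows by 25%. The sum goes from 5P to 1.25P, and 1.25/5 = 25%, a fall of 75%. That passes the 50% cut on the sum, but the growing lesion makes the patient PD. Suppose SUV falls by at least 25% in the four and rises in the fifth, so the scans agree on every lesion. The patient is an FLT responder if the value comes from a hottest baseline lesion among the four, and a non-responder if every lesion must decline. The plan does not say which rule applies.

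**2. Discordance from roll-up alone.** ICC is the within-patient intraclass correlation.

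- *Log-ratio model.* Lesion log-ratios are N(-1.15, SD 0.9) for MRI product and N(-0.5, SD 0.5) for SUV. MRI response means the sum falls by at least 50% with no lesion up 25%. FLT follows the patient's maximum SUV. With perfect lesion-level correlation, discordance is 3% with one lesion, 15-19% with three and 17-23% with five (ICC 0.3-0.6). The 3% comes from the cut-points: (ln 0.5 + 1.15)/0.9 = 0.51 gives 69% MRI response, and (ln 0.75 + 0.5)/0.5 = 0.42 gives 66% FLT response.
- *Yes/no model.* Each lesion's response is identical on both scans, at a rate of 65-70%, with no progression veto. With one lesion, discordance is 0%. With three lesions and a hottest-lesion or patient-maximum rule, it is 17-20% at ICC 0.3, 12-14% at 0.5 and 7-9% at 0.7. For three to five lesions and ICC 0.3-0.7, other FLT rules give 3-11% (largest lesion), 5-15% (mean), 7-29% (all lesions) and 12-34% (any lesion).

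**3. How much realistic discordance is roll-up?** In the log-ratio model at correlation 0.6, discordance is already 26% with one lesion. With three it is 30-33%, so roll-up adds 30 - 26 = 4 to 33 - 26 = 7 points. If 15% of patients also have a new lesion, discordance is 35-37%.

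**4. Power to detect an association (log-ratio model, n=20, correlation 0.6, ICC 0.3-0.6).** The table is tested with Fisher's exact test, because McNemar's test compares the two marginal response rates. With 30% of patients discordant each way (60% disagreement), exact McNemar rejects only 2% of the time.

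| Analysis | 1 lesion | 3 lesions |
|---|---|---|
| 2x2 table | 29-34% | 17-25% |
| Continuous, patient level | 77% (Spearman), 83% (Pearson) | 82-83% (mean log-change); 52-64% (hottest lesion against sum) |
| Lesion level, patient-clustered | no further lesions to use | 97-100% |

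With three lesions, moving from the table to the patient mean log-change gains 82 - 25 = 57 to 83 - 17 = 66 points. Moving on to lesion level gains a further 97 - 83 = 14 to 100 - 82 = 18. Dichotomising is the main loss. At correlation 0.4 with three lesions, the table has 7-11% and the lesion-level analysis 71-83%.

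**5. Information from extra lesions.** Effective N = 20m/(1 + (m-1) x ICC) for m lesions per patient. For m=3 and ICC 0.3, 60/1.6 = 37.5; for m=3 and ICC 0.7, 60/2.4 = 25; for m=5 and ICC 0.3, 100/2.2 = 45; for m=1, 20. Clustering alone costs the patient-level analysis more than half the information only if ICC is below 0.25 (three lesions) or 0.375 (five).

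**The case against.** The strongest reply is that "This is a small pilot study involving 20 patients with brain metastases from breast cancer", mainly descriptive, with an FLT-MRI comparison that is secondary and introduced as something to explore. No power is claimed. Secondary objective 1 concerns response in patients, and there a new lesion properly counts as progression. All of this stands. It limits the weight of the point and is why the patient-level comparison should stay.

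Four stronger readings are tempting, and the documents do not support them.

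- A reader might infer that most of the concordance information is lost by ignoring lesions. That depends on a lesion count and an ICC that the plan does not give, and Section 6.2 admits single-lesion patients, for whom nothing is lost that way.
- A reader might infer that discordance is built in. It is 0-3% with one lesion. At a realistic correlation most of it comes from imperfect correlation and two cut-points.
- A reader might infer two known but unlike roll-up rules, with FLT resting on one voxel in the hottest lesion and five lesions followed on each scan. The five-lesion limit is an MRI rule only, and the FLT rule is missing.
- A reader might infer that nothing but a yes/no comparison is planned. The boxplots keep SUV continuous, although they are descriptive and group patients by one MRI status each.

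**Conclusion.** The point holds in a limited form. The only formal FLT-MRI comparison uses one binary value per patient per modality, and the rule that produces the FLT value in a multi-lesion patient is not stated. Under the assumed correlation of 0.6, dichotomising takes power from about 80% to about 30% even with one lesion per patient. In multi-lesion patients, roll-up alone can make about 15-20% discordant with three lesions, a hottest-lesion FLT rule and ICC 0.3-0.6. The figure is lower at higher ICC and varies with the FLT rule.

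The true correlation, lesion count, ICC, log-ratio distributions and baseline spread are all assumptions, so the figures show direction and rough size only. Nothing here invalidates the descriptive aims. It is a cheap improvement to an exploratory secondary comparison.

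**What to change.** In Sections 12 and 14.0:

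1. Keep the patient-level comparison for secondary objective 1, and state which lesions are measured on FLT and how their SUVs become one patient value.
2. Add a continuous analysis of log-ratio change in SUVmax against log-ratio change in product of diameters, baseline to 10-12 weeks. Do this at patient level, and at lesion level for lesions measured on both scans. Use a random patient effect or a patient-cluster bootstrap, with a small-sample correction. This carries the question of association, which McNemar's test does not address.
3. Fix in advance the value used when a lesion disappears, since a zero product has no log-ratio.
4. Report new lesions separately.

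No new scans are needed. The cost is some image-analysis work: the summary at the end of Section 10.1.2 identifies tumour on the CT of the PET/CT, so PET and MRI lesions must be matched and labelled consistently. Single-lesion patients gain only from the continuous scale. With 20 clusters the uncorrected clustered test is slightly liberal (6-8% at a nominal 5% in the simulation), hence the correction.

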2.1 OBJECTIVES AND SCIENTIFIC AIMS

Primary Objective: The primary objectives of this study are as follows:

- 1) To examine the radiographic response to WBRT by FLT-PET and MRI for each cohort of 10 patients separately.
- 2) To examine and quantify changes in response as assessed by serial FLT PET images taken over the course of treatment for each cohort of 10 patients separately.

Secondary Objectives: The secondary objectives of this study are as follows:

- 1) To correlate treatment response as measured by FLT-PET with response assessment based on MRI of the brain in all patients and assess duration of response (i.e., CNS progression-free survival) during follow-up with MR imaging.

Exploratory Objective: The exploratory objectives of this study are as follows:

- 1) To correlate the ability of FLT-PET and MRI of the brain imaging to differentiate viable tumor, inflammation and necrosis with surgical resection specimens (if available) obtained in patients with a medical indication for craniotomy.

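### Section 14 specifies no estimate of the FLT-MRI correlation named in secondary objective 1: both measures are cut to yes/no, McNemar's test compares response rates, and no analysis of measured MRI size change is named.

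*Combined protocol and SAP*

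**What the plan says.** Section 2.1 gives secondary objective 1 as: "To correlate treatment response as measured by FLT-PET with response assessment based on MRI of the brain in all patients".

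Section 12 measures MRI response on a continuous scale. Section 12.1 bases objective response on "comparison of the changes in the product of the largest perpendicular measurements of the lesion at each visit", and Section 12.3 uses the sum of those products to define PR. The measurements are then used to assign CR, PR, SD, PD or unknown.

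Section 14.0 carries forward the categories. For the descriptive part, "the distribution of response at baseline and the 10-12 week post WBXRT timepoint as assessed by MRI and FLT-PET will be examined". For the comparison of modalities, the frequency of a 25% SUV decline, taken as yes or no for each patient, "will be calculated in the following two MRI response groups: CR+PR vs. PD+SD". McNemar's test follows, described as a test of agreement. The same paragraph adds boxplots of SUV for each MRI category, by cohort, and cites a 65-70% MRI response rate from the literature.

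SUVmax and the kinetic parameters get median, mean, minimum and maximum at each timepoint. MRI size gets no such summary. Section 14.0 also has a general sentence that data from each modality will be looked at descriptively and graphically. It states no alpha, power or expected correlation.

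**The concern.** The objective asks how closely two measures move together, and the specified analysis does not answer that. There are two separate reasons.

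- **The test.** McNemar's test asks whether the proportion responding on FLT equals the proportion responding on MRI. Those proportions can be equal with perfect association or with none.
- **The variables.** Both sides are cut in two. On the MRI side, a 45% shrinkage (SD under Section 12.3) is grouped with a doubling (PD) and separated from a 50% shrinkage (PR). At the cited response rate only 6 or 7 of 20 patients fall in PD+SD, so any association in the table rests on them.

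At stake is whether the pilot yields a usable estimate, with its uncertainty, of the quantity a later study would need. With 20 patients, recorded information is costly to discard.

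**Working it through.** **Inputs.** From the documents: 20 patients in two cohorts of 10, the objective in all patients, a 65-70% MRI response rate, and both variables binary in the comparison. Assumed, because the documents give no figure: two-sided 5%, bivariate normal changes, true correlation 0.3 to 0.7, 60% FLT responders where FLT is cut, and 15% of patients tied at the best MRI rank (CR) and 15% at the worst (PD). There is no design figure in the plan to reproduce.

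**1. What McNemar's test sees.** Take 14 of 20 (70%) responding on each modality.

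| | Both | MRI only | FLT only | Neither | Same result | Phi |
|---|---|---|---|---|---|---|
| Table A | 14 | 0 | 0 | 6 | 20/20 | (14×6 − 0×0)/84 = 1.00 |
| Table B | 10 | 4 | 4 | 2 | 12/20 | (10×2 − 4×4)/84 = 0.05 |

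The denominator is √(14×6×14×6) = 84. McNemar's test uses only the two discordant counts. They are equal in both tables, so the difference in response rates is 0 and the exact p-value is 1 in both. One table has perfect association and the other almost none.

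Simulation at n=20 agrees. With 67.5% responders on both modalities, exact McNemar rejects 2.0%, 1.5% and 0.3% of the time at true correlations 0, 0.5 and 0.8. With 67.5% on MRI and 90% on FLT it rejects 23.6%, 26.7% and 28.2%. The result follows the gap in rates, not the correlation.

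**2. What cutting MRI costs in information.** 65-70% of 20 leaves 13-14 patients in CR+PR and 6-7 in PD+SD. Cutting a normal variable at responder proportion p multiplies its correlation by φ(z)/√(p(1−p)), where z is the normal quantile of p.

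- p = 0.65: 0.370/0.477 = 0.78; squared, 0.60; 20 × 0.60 = 12
- p = 0.70: 0.348/0.458 = 0.76; squared, 0.58; 20 × 0.58 = 11.6

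For small correlations, MRI in two groups therefore carries about as much information as 12 patients measured on a full scale. This is an upper figure for the loss, because ties at CR and PD would take something from the full scale too.

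**3. The same loss as power, with those ties included.** FLT is kept continuous in both analyses to isolate the MRI cut: Wilcoxon by MRI group (67.5% responders) against Spearman with MRI ranked.

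| True correlation | MRI in two groups | MRI ranked | Difference |
|---|---|---|---|
| 0.3 | 15% | 23% | 8 |
| 0.4 | 24% | 36% | 12 |
| 0.5 | 36% | 56% | 20 |
| 0.6 | 53% | 75% | 22 |
| 0.7 | 70% | 92% | 22 |

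Repeat runs gave about 7 points at 0.3 and up to 25 points at 0.6. Null rejection rates were 4.4% and 5.6%. With the two tests matched in size, the differences at 0.4 to 0.7 are about 11, 17, 22 and 18 points.

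**4. Sensitivity.** With FLT cut as well, Fisher's test on the 2×2 table has power 13%, 19%, 31% and 46% at 0.4 to 0.7. If FLT stays binary with the same responder rate as MRI and an uncorrected chi-square is used, the cost of the MRI cut is only 5 to 15 points at 0.4 to 0.6. Patients with a negative baseline FLT-PET leave the study, so fewer than 20 may be evaluable; at 16, the comparison at 0.6 is 43% against 64%.

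**5. What the added estimate would give.** By Fisher's z, an approximation for Spearman, an observed 0.5 in 20 patients has limits of tanh(0.549 ± 1.96/√17), or 0.07 to 0.77.

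**The case against.** The strongest reply is that this is a descriptive pilot which says its sample limits its analyses, promises no power, and only sets out to explore whether the modalities correlate. That stands. It is why the loss is better stated as precision, and why the power figures are only an illustration.

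Three stronger readings are tempting, and the documents do not support them.

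- A reader might infer that MRI size change will never be examined. The general descriptive sentence in Section 14.0 could cover it. What can be said is that no such analysis is specified.
- A reader might infer that the plan cannot tell SD from PD. The boxplots keep every MRI category apart and leave SUV continuous. They do, however, plot SUV rather than MRI size change, spread about 10 patients per cohort over several categories, and give no measure of association.
- A reader might infer that the planned test loses 12 to 25 points of power. The planned test is McNemar's, which does not target correlation. The figures compare two other tests, under assumed correlations and responder rates.

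Percent change is also not a full substitute for the Section 12.3 category. That category takes in steroid use, neurological status, and new or evaluable lesions, and PD can come from one growing lesion while the sum falls. This stands, and it is why the categories should be kept.

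**Conclusion.** The point holds as a mismatch between objective and analysis. Secondary objective 1 calls for a correlation; Section 14.0 specifies two binary variables and a comparison of response rates, with no correlation estimate and no analysis of the recorded MRI size change. The mismatch rests on the text alone and needs no simulation.

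The size of the loss depends on assumptions. Under those listed above, putting MRI in two groups lowers power by about 7 points at a true correlation of 0.3 and about 12 to 25 points at 0.4 to 0.7, or in information terms leaves roughly 12 patients' worth out of 20. The amount changes with the true correlation, the choice of test and the FLT responder rate, none of which the documents settle. Even the better analysis has only about 36% power at 0.4, so the reason to adopt it is an interpretable estimate with an interval, not a reliable test. The change is worth making because it is inexpensive and serves a stated objective, but the descriptive pilot does not fail without it.

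**What to change.** In Section 14.0:

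- Add, for secondary objective 1, a Spearman correlation with a 95% CI and a scatterplot of percent change in the MRI sum of products against percent change in SUVmax, both from baseline to 10-12 weeks, in all patients.
- State the ranking rule: complete disappearance ranks best; every PD patient ranks worst, whether from a new lesion, an evaluable lesion or growth in a single lesion; patients with unknown status are left out and counted.
- Add median, minimum and maximum of percent MRI change by cohort, as is already done for SUV.
- Keep the CR+PR vs PD+SD table and the boxplots, and describe McNemar's test as a comparison of response rates.

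The cost is wording. The diameters are already recorded to apply Section 12, and no scan or visit is added. The downsides are that a ranking convention has to be fixed in advance and that percent change does not reflect steroid use or neurological status; the retained category table does.

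### McNemar's test is labelled a test of agreement between FLT-PET and MRI, but it compares only the two response rates and cannot show whether the same patients respond on both scans

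*Combined protocol and SAP*

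**What the plan says.** Secondary objective 1 (section 2.1) is "To correlate treatment response as measured by FLT-PET with response assessment based on MRI of the brain in all patients". Section 14.0 takes this up as exploratory: "we will explore whether treatment response for the two modalities correlate".

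The two binary variables are defined there. For FLT-PET: "FLT-PET response assessments will be recorded as SUV-MAX and a decline by 25% is considered as significant". MRI response is grouped as CR+PR against PD+SD. Three analyses follow:

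- **Descriptive proportions.** The FLT-PET summary is "the proportion of patients with significant change in SUV (FLT-PET) as a dichotomous variable", taken separately within each of these MRI groups.
- **The formal test.** "The McNemar's test for paired samples will be done to test the agreement of the two modalities".
- **Plots.** "boxplots of SUV will be graphed for each MRI response category for each cohort".

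On expected rates, section 14.0 says only that "there is a 65-70 percent response rate as per MRI". It gives no expected FLT-PET response rate, no alpha, and no statement of how a non-significant McNemar result will be read. Overall agreement, kappa and confidence intervals are not planned.

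**The concern.** The question posed is about individual patients: does a patient who responds on one scan also respond on the other? McNemar's null hypothesis is about margins: is the proportion responding the same on both scans? The test ignores the patients on whom the scans agree. Two scans can have identical response rates while picking out different patients, and two scans can classify most patients alike while one of them systematically calls fewer responders.

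This is the only p-value in the plan, and it carries the label of agreement. With 20 patients and similar response rates, p > 0.05 is the likely outcome whether or not the scans agree. Under that label it invites the conclusion that FLT-PET agrees with MRI, which the test cannot support. It could also contradict the proportions reported beside it.

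**Working it through.** **Inputs from the documents.** N = 20, in two cohorts of 10 (section 14.0); MRI response rate 65-70% (section 14.0), i.e. 13 or 14 of 20; FLT-PET response = 25% decline in SUVmax; MRI response = CR+PR.

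**Assumptions.** Two-sided alpha 0.05, a range of FLT-PET rates, and all 20 patients evaluable on both scans. The plan has no figure of its own for this test, so there is nothing to reproduce.

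**Formulas.** Let a = both respond, b = FLT only, c = MRI only, d = neither.

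- Exact McNemar p = min{1, 2 × P[X ≤ min(b, c)]}, with X ~ Binomial(b + c, 0.5). Neither a nor d enters.
- Observed agreement po = (a + d)/n.
- Chance agreement pe = [(a + b)(a + c) + (c + d)(b + d)]/n².
- Kappa = (po − pe)/(1 − pe).

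**Step 1: same p-value, very different agreement.** In the first three tables each scan has 13 responders, so pe = (13² + 7²)/400 = 0.545.

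| a/b/c/d | Agreement | Kappa | Exact p | SUV responders: CR+PR vs PD+SD |
|---|---|---|---|---|
| 13/0/0/7 | 100% | 1.00 | 1.0 | 13/13 vs 0/7 |
| 11/2/2/5 | 80% | (0.80 − 0.545)/0.455 = 0.56 | 1.0 | 11/13 vs 2/7 |
| 7/6/6/1 | 40% | (0.40 − 0.545)/0.455 = −0.32 | 1.0 | 7/13 vs 6/7 |
| 7/0/6/7 | 70% | (0.70 − 0.455)/0.545 = 0.45 | 0.031 | 7/13 vs 0/7 |

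Perfect agreement and worse-than-chance agreement give the same p. This needs no choice of alpha. The last column, which the plan already intends to report, does separate the tables.

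**Step 2: the ordering can reverse.** In the fourth row MRI responds in 13/20 and FLT in 7/20, so pe = (7 × 13 + 13 × 7)/400 = 0.455 and p = 2 × 0.5⁶ = 0.031. Agreement is much better than in the third row, yet this is the table that would be rejected. The exact test needs at least six discordant patients, all in one direction, to fall below 0.05 when discordance is one-sided (five give 0.0625).

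**Step 3: behaviour when the scans are unrelated.** Under independence, P(FLT only) = FLT × (1 − MRI) and P(MRI only) = MRI × (1 − FLT). Full enumeration at n = 20 gives the probability of a non-significant result:

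| True FLT rate | MRI 0.65 | MRI 0.70 |
|---|---|---|
| 0.40 | 77% | 66% |
| 0.50 | 91% | 85% |
| Equal to MRI | 98% | 98% |
| 0.80 | 90% | 95% |
| 0.90 | 70% | 81% |

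Scans with no relation to each other would therefore usually pass the test.

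**Step 4: varying true agreement.** With both rates at 0.65, the test is non-significant in 97.6% of trials at true kappa −0.3, 97.9% at 0 and 99.7% at 0.6: it barely responds to agreement. With MRI 0.70 and FLT 0.40, raising true kappa from 0 to 0.4 lowers non-significance from 66% to 45%, so rejection rises from 34% to 55% as agreement improves.

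**The case against.** The strongest reply is that little depends on this. The study is a pilot of 20, the analysis is secondary and called exploratory, no decision rule uses the p-value, and section 1.0 says the FLT scans do not affect patient management. The planned proportions, together with the group counts, give the whole 2×2 table, from which agreement and kappa can be computed. Nothing in the plan says that p > 0.05 will be read as agreement, and a paired comparison of response rates is a legitimate part of comparing two modalities. All of this stands and limits the severity. It does not repair a test labelled with a question it does not answer.

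The reversal in step 4 also needs context. It assumes a true 30-point difference in rates. At those margins the largest possible kappa is (0.70 − 0.46)/0.54 = 0.44, and rejection there is McNemar's test correctly detecting unequal rates. That supports the point: the test answers the question about rates.

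The percentages would change with fewer evaluable pairs, since patients negative on baseline FLT-PET leave the study and MRI status can be unknown. At n = 15, for example, the 66% for MRI 0.70/FLT 0.40 becomes 77%. The principle does not change.

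Finally, section 12.3 defines CR and PR on consecutive scans at least a month apart, while only one post-WBRT MRI is scheduled by 10-12 weeks. That is a separate question. It affects the plan's own CR+PR grouping as much as any replacement analysis.

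**Conclusion.** The concern holds and should be fixed. As written, the plan would report a p-value for agreement that does not measure agreement. At equal response rates of 65%, p = 1.0 is compatible with kappa anywhere from 1.00 to at least as low as −0.32. If the scans were independent, the exact test would be non-significant in 98% of trials at equal rates, 85-98% for FLT rates of 0.50-0.80, and 66-98% for 0.40-0.90.

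The example tables rest only on N = 20 and a 65% rate. The trial-level percentages also assume two-sided alpha 0.05, the stated FLT rates and complete pairs. The flaw is limited to the formal test for secondary objective 1 and its label. The proportions and boxplots remain useful, and the primary objectives are descriptive and unaffected.

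**What to change.** Replace the McNemar sentence in section 14.0 with wording such as:

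> At 10-12 weeks, FLT-PET response (25% decline in SUVmax) and MRI response (CR+PR versus SD+PD) will be cross-tabulated in patients assessed on both. Overall, positive and negative percent agreement (MRI as reference) with exact 95% confidence intervals, and Cohen's kappa with a 95% confidence interval, will be reported as estimates, without a hypothesis test of agreement.

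Positive and negative agreement follow directly from the proportions already planned; the additions are overall agreement, kappa and the intervals. Taking MRI as reference only follows the plan's own conditioning on MRI group and need not imply that MRI is the truth. The text should also say how an unknown MRI status is handled and that kappa is imprecise at n = 20. Half the central 95% range of the kappa estimate was 0.30 to 0.44 across the scenarios simulated, so the 95% half-width is about 0.3-0.45.

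If McNemar's test is kept, label it a comparison of the two response rates and state that p > 0.05 is not evidence of agreement. Optional additions are Fisher's exact test on the 2×2 table as a test of association, and the Spearman correlation of percent change in SUVmax with percent change in the MRI sum of products.

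The cost is a short change to the analysis section and a few lines of code on data already collected, with no extra patients or procedures.
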